9.3.2. All-cause HCRU and Costs Over the Post-Index Period (Post-IPTW)

All-cause HCRU and costs will be reported for the Apixaban and LMWH cohorts over the variable post-index period (minimum 1 month enrollment), post-IPTW. Costs will be reported

PFIZER CONFIDENTIAL

CT24-WI-GL02-RF02 4.0 Non-Interventional Study Protocol Template For Secondary Data Collection Study 01-Jun-2022

Page 23 of 35

090177e19b7d94e0\Approved\Approved On: 29-Aug-2023 01:40 (GMT)

Apixaban

B0661183 NON-INTERVENTIONAL STUDY PROTOCOL

Protocol Version: 2.0 29 July 2022

as per patient per month (PPPM). Over the post-index period, a 30 day period will be used (to represent a month) to ‘standardize’ the period of time for which costs and HCRU will be reported. For each patient, costs will be divided by the variable post-index period in total-person days and then multiplied by 30 to calculate PPPM costs. For example, if a patient has total costs of \$10,000 with 60 days of follow-up, the PPPM will be calculated as $(\$10,000/60) * 30 = \$5,000$.

HCRU will be expressed as both the proportion of patients with such utilization (e.g., the percentage of patients with at least one pharmacy claim, the percentage of patients with at least one physician office visits, etc.) as well as per-patient mean, SD, median and IQR number of visits/services. Costs will be expressed as per-patient mean, SD, median and IQR. Utilization and costs will be calculated on a per patient basis, averaged across the cohort. The denominator will include all patients in the cohort. Costs will be converted to 2021 US dollars (USD) using the medical component of the Consumer Price Index.

HCRU and costs will be reported for mutually exclusive categories: outpatient pharmacy, inpatient hospitalizations, and outpatient care. Outpatient care will comprise the following categories: ER visits, outpatient physician office visits, outpatient surgical visits, laboratory and pathology, radiology and all other services.

All-cause HCRU and costs will be reported for each of the following services:

- Pharmacy
 - Patients with ≥ 1 prescription fill (n, %)
 - Number of prescription fills per patient (mean, SD, median, IQR)
 - Total pharmacy cost per patient (mean, SD, median, IQR)
- Outpatient Services
 - Total outpatient medical care cost per patient (mean, SD, median, IQR)
 - Physician office visits
 - Patients with ≥ 1 physician office visit (n, %)
 - Number of physician office visits per patient (mean, SD, median, IQR)
 - Total physician office cost per patient (mean, SD, median, IQR)
 - ER only visits (ER visit without admission to hospital)
 - Patients with ≥ 1 ER visit (n, %)
 - Number of ER visits per patient (mean, SD, median, IQR)
 - Total ER cost per patient (mean, SD, median, IQR)
 - Laboratory/pathology tests
 - Patients with ≥ 1 laboratory test (n, %)
 - Number of laboratory tests per patient (mean, SD, median, IQR)

PFIZER CONFIDENTIAL

CT24-WI-GL02-RF02 4.0 Non-Interventional Study Protocol Template For Secondary Data Collection Study 01-Jun-2022

Page 24 of 35

090177e19b7d94e0\Approved\Approved On: 29-Aug-2023 01:40 (GMT)

Apixaban

B0661183 NON-INTERVENTIONAL STUDY PROTOCOL

Protocol Version: 2.0 29 July 2022

-
- Total laboratory cost per patient (mean, SD, median, IQR)
 - Radiology
 - Patients with ≥ 1 outpatient radiology exam (n, %)
 - Number of outpatient radiology exams per patient (mean, SD, median, IQR)
 - Total radiology cost per patient (mean, SD, median, IQR)
 - Surgical services
 - Patients with ≥ 1 outpatient surgical visit (n, %)
 - Number of outpatient surgical visits per patient (mean, SD, median, IQR)
 - Total outpatient surgical visit cost per patient (mean, SD, median, IQR)
 - Ancillary/other services
 - Patients with ≥ 1 outpatient ancillary/other service (n, %)
 - Number of outpatient ancillary/other services per patient (mean, SD, median, IQR)
 - Total outpatient ancillary/other cost per patient (mean, SD, median, IQR)
 - Total HCPCS drug cost per patient (mean, SD, median, IQR)
 - Inpatient hospitalizations
 - Patients with ≥ 1 hospitalization (n, %)
 - Average length of stay per patient for all hospitalizations (mean, SD, median, IQR)
 - Number of hospitalizations per patient (mean, SD, median, IQR)
 - Total hospitalization days per patient (mean, SD, median, IQR)
 - Top 10 primary discharge diagnosis associated with the first hospitalization, overall (ICD 10-CM 3-digit level; n, %)
 - Total inpatient cost per patient (mean, SD, median, IQR)
 - Number of hospitalizations per patient (mean, SD, median, IQR)
 - Total inpatient cost per patient (mean, SD, median, IQR)
 - Total all-cause cost per patient (total pharmacy + total outpatient + total inpatient; mean, SD, median, IQR)

PFIZER CONFIDENTIAL

CT24-WI-GL02-RF02 4.0 Non-Interventional Study Protocol Template For Secondary Data Collection Study 01-Jun-2022

Page 25 of 35

090177e19b7d94e0\Approved\Approved On: 29-Aug-2023 01:40 (GMT)

Apixaban

B0661183 NON-INTERVENTIONAL STUDY PROTOCOL

Protocol Version: 2.0 29 July 2022

9.3.3. Recurrent VTE, major bleeding, and CRNM bleeding related HCRU and costs in the post-index period

Recurrent VTE will be identified based on inpatient claims with VTE as the primary discharge diagnosis (ICD-10 diagnosis codes). If the admissions for recurrent VTE occur within 7 days of the index VTE event, irrespective of care setting, the events will not be considered as recurrent VTE events due to the proximity to the index VTE event and the index date.

Major bleeding will be defined by primary discharge diagnosis in the inpatient setting, including GI bleeding, intracranial hemorrhage (ICH), and other major bleeding.

CRNM bleeding will be defined as an inpatient encounter with a secondary diagnosis code for bleeding (without a major bleeding code in the primary position) or an outpatient encounter with a diagnosis code in any position for CRNM GI bleeding or other non-critical types of bleeding. **Error! Bookmark not defined. Error! Bookmark not defined.** Specifically, it is defined as:

- (1) An inpatient admission with a secondary diagnosis for “noncritical site” bleeding such as GI bleeding or other selected noncritical types/sites of bleeding (excluded if major bleeding occurred during the same hospitalization), OR
- (2) An outpatient encounter with a diagnosis code for GI bleeding and other selected noncritical types/sites of bleeding.

Any CRNM bleeding events (as described above) that follow a major bleeding event (described above) will not be included in the analysis of CRNM bleeding.

For the two therapy cohorts, the following outcomes related to recurrent VTE, major bleeding and CRNM will be reported post-IPTW.

- Recurrent VTE across the cohort
 - Patients with ≥ 1 such event (n, %)
 - Number of hospitalizations for VTE events (denoted by inpatient hospitalizations that meet the definition above) (mean, median, SD, IQR)
 - Time (in days) from index date to first recurrent VTE event (mean, median, SD, IQR)
- Major bleeding across the cohort
 - Patients with ≥ 1 such event (n, %)
 - Number of hospitalizations for major bleeding events (denoted by inpatient hospitalizations that meet the definition above) (mean, median, SD, IQR)
 - Time (in days) from index date to first major bleeding event (mean, median, SD, IQR)
- CRNM bleeding across the cohort
 - Patients with ≥ 1 such event (n, %)

PFIZER CONFIDENTIAL

CT24-WI-GL02-RF02 4.0 Non-Interventional Study Protocol Template For Secondary Data Collection Study 01-Jun-2022

Page 26 of 35

090177e19b7d94e0\Approved\Approved On: 29-Aug-2023 01:40 (GMT)

Apixaban

B0661183 NON-INTERVENTIONAL STUDY PROTOCOL

Protocol Version: 2.0 29 July 2022

- Number of CRNM bleeding events (denoted by inpatient or outpatient events that meet the definition above) (mean, median, SD, IQR)
- Time (in days) from index date to first CRNM bleeding event (mean, median, SD, IQR)

The Cost, and HCRU, for each event will be defined as the cost associated with the hospitalization for the respective event (i.e., recurrent VTE, MB, or CRNM bleeding) as well as all subsequent event-related medical costs (pharmacy costs will not be included). These can be determined via an appropriate diagnosis code that relates to the event of interest. Major bleeding-related medical costs will be defined as costs associated with the first major bleeding hospitalization plus all subsequent bleeding costs occurring in the inpatient (primary or secondary diagnosis) or outpatient setting (any position). Recurrent VTE-related medical costs will be defined as the costs associated with the first recurrent VTE hospitalization plus all subsequent VTE costs in the inpatient (primary or secondary diagnosis) or outpatient (any position) setting. Similarly, CRNM bleeding-related medical costs will be defined as hospitalization costs or outpatient costs associated with the first CRNM bleeding as defined above and all the subsequent CRNM bleeding costs in the inpatient (primary or secondary diagnosis) or outpatient (any position) setting.

The outpatient services and inpatient hospitalization HCRU and cost variables presented in section 8.3.2 will also be reported for recurrent VTE-related, major bleeding-related and CRNM bleeding-related utilization and costs.

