8. RESEARCH QUESTION AND OBJECTIVES

The purpose of this study is to evaluate the costs and HCRU associated with treating VTE cancer patients with apixaban compared to LMWH (dalteparin, enoxaparin, or tinzaparin).

The objectives of the study are as follows:

Primary objectives:

- To compare all-cause healthcare costs among VTE patients with cancer treated with apixaban vs LMWH
- To compare costs associated with recurrent VTE, major bleeding, and clinically relevant non-major (CRNM) bleeding among VTE patients with cancer treated with apixaban vs LMWH

Secondary objectives:

- To compare all-cause HCRU among VTE patients with cancer treated with apixaban vs LMWH
- To compare HCRU associated with recurrent VTE, major bleeding, and CRNM bleeding among VTE patients with cancer treated with apixaban vs LMWH

090177e19b7d94e0\Approved\Approved On: 29-Aug-2023 01:40 (GMT)

PFIZER CONFIDENTIAL

CT24-WI-GL02-RF02 4.0 Non-Interventional Study Protocol Template For Secondary Data Collection Study 01-Jun-2022

Page 15 of 35

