9.1. Study period and study design

The analysis will be conducted using data from 01 January 2016 through 31 December 2021 or the latest available data at the time of extraction (i.e., the *study period*). Patients will be identified during a *selection window* of 01 January 2017 to 31 October 2021. The date of the first apixaban or LMWH prescription on or within the 30 days following a VTE diagnosis will be termed as the index date. Patients will be required to have continuous enrollment with medical and pharmacy benefits for 12-months prior to the index date to assess study eligibility criteria and to measure baseline characteristics (*the baseline or pre-index period*). Patients will also be required to have continuous enrollment with medical and pharmacy benefits for at least one month (30 days) starting on and following the index date (the follow-up or post-index period) and will be followed through the earliest of the following: health plan disenrollment, index therapy discontinuation, switch to another anticoagulant (includes switch to the other study medication or unfractionated heparin, fondaparinux, warfarin, rivaroxaban, dabigatran, or edoxaban), or end of study period (31 December 2021).

Note: Patients in the LMWH cohort will NOT be considered to have discontinued or switched if they change to an LMWH other than the index LMWH (dalteparin, enoxaparin, or tinzaparin).

Figure 1. Study Period

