9.1.1. Inclusion criteria

Patients must meet all of the following inclusion criteria to be eligible for inclusion in the study:

090177e19b7d94e0\Approved\Approved On: 29-Aug-2023 01:40 (GMT)

Apixaban

B0661183 NON-INTERVENTIONAL STUDY PROTOCOL

Protocol Version: 2.0 29 July 2022

1. Patients with ≥ 1 diagnosis code for VTE (inpatient [primary or secondary discharge diagnosis] or any position on an outpatient non-ancillary medical claim) between January 1, 2017 and October 31, 2021 (selection window).
 - Note: Qualifying outpatient encounters followed by qualifying inpatient encounters within 7 days will be considered an inpatient VTE event, unless LMWH or apixaban was initiated between encounters, in which case it will be classified as an outpatient VTE event
 - First date of claim with a VTE diagnosis code will be termed the ‘index VTE encounter’

2. Evidence of having active cancer, defined as ≥ 2 medical claims with a cancer diagnosis (excluding nonmelanoma skin cancer) on different days during the 6 months before or within 30-days after the index VTE event

OR

≥ 1 medical claim for a cancer diagnosis AND ≥ 1 claim for cancer treatment (eg: chemotherapy, radiation, immunotherapy, hormone therapy or cancer related surgery using national drug codes (NDC), international classification of diseases, tenth revision, clinical modification [ICD-10-CM] procedure codes or healthcare common procedure coding system [HCPCS] codes) during 6 months before or within 30 days after the index VTE encounter

3. ≥ 1 claim of apixaban or LMWH (dalteparin orenoxaparin) on or within 30 days following the index VTE encounter.
 - a. The date of the first apixaban or LMWH prescription fill will be designated as the index date
4. ≥ 12 months of continuous enrollment prior to the index date (pre-index)
5. ≥ 1 months of continuous enrollment including and following the index date (post-index)
 - a. Note: Each patient will have a variable follow-up period with a minimum of 1-month follow-up. Patients will be followed from the day after the index date through the earliest of the following: health plan disenrollment, index therapy discontinuation, switch to another anticoagulant, or study end (December 31, 2021).
 - b. Discontinuation will be defined as occurrence of a ≥ 30 day gap from the run-out of days’ supply of the index LMWH or apixaban prescription. The date of the discontinuation will be defined as the last day of the days’ supply of the last filled prescription.

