9.3.1. Baseline Measures

Baseline demographic/clinical characteristics will be descriptively reported for the Apixaban and LMWH cohorts, both pre- and post-IPTW. Demographic characteristics will be measured as of the patient's index date while clinical characteristics will be measured over the 1-year pre-index baseline period.

Demographic Characteristics

- Age (mean, standard deviation [SD], median, interquartile range [IQR])
- Age group (18-24, 25-34, 35-44, 45-54, 55-64, 65-74, ≥ 75 years; n, %)
- Gender (male, female, unknown/missing; n, %)
- Geographic region (Northeast, Midwest, South, West, unknown/missing; n, %)
- Payer type (commercial, Medicaid, Medicare Risk, self-insured, other/unknown; n, %)
- Health plan type (consumer directed health care, health maintenance organization [HMO], indemnity, point-of-service [POS], preferred provider organization [PPO], other/unknown; n, %)

PFIZER CONFIDENTIAL

CT24-WI-GL02-RF02 4.0 Non-Interventional Study Protocol Template For Secondary Data Collection Study 01-Jun-2022

Page 19 of 35

090177e19b7d94e0\Approved\Approved On: 29-Aug-2023 01:40 (GMT)

Apixaban

B0661183 NON-INTERVENTIONAL STUDY PROTOCOL

Protocol Version: 2.0 29 July 2022

- Index date year (2017, 2018, 2019, 2020, 2021; n, %)
- Follow up duration in months (mean, SD, median, IQR)
 - Patients censored due to switching (n, %)
 - Patients censored due to discontinuation (n, %)

Clinical Characteristics

- Prescriber physician specialty (associated with the visit on or closest to the index date, as available) (n, %)
 - Primary care physician (PCP - general practice/family practice/internal medicine)
 - Cardiologist
 - Oncologist
 - Others
 - Unknown/missing
- Index VTE event setting (n, %)
 - Inpatient
 - Total inpatient cost of index VTE hospitalization (mean, SD, median)
 - Length of stay (LOS) of index hospitalization (mean, SD, median)
 - Outpatient
 - Note: Qualifying outpatient encounters followed by qualifying inpatient encounters within 7 days will be considered an inpatient VTE event, unless LMWH or apixaban was initiated between encounters, in which case it will be classified as an outpatient VTE event
- Index VTE type (n, %)
 - DVT
 - PE
 - DVT and PE
- Charlson Comorbidity Index (CCI, Dartmouth-Manitoba adaptation excluding cancer; continuous and categorical [0-1, 2, 3, 4+]) (n, %)
- NCI comorbidity index (continuous and categorical [0-1, 2, 3, 4+]) (n, %)
- Comorbidities of interest (ICD-10 diagnosis codes; n, %)

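### Whole-period cost per month mixes drug cost with time on drug: unless cost is flat over time or persistence is equal, the cohorts' PPPM values differ even when cost is identical at every time point

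*Combined protocol and SAP*

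**What the plan says.** The first primary objective (section 8) is "To compare all-cause healthcare costs among VTE patients with cancer treated with apixaban vs LMWH". Section 9.3.2 defines the measure: "For each patient, costs will be divided by the variable post-index period in total-person days and then multiplied by 30 to calculate PPPM costs". It then says how patients are combined: "Utilization and costs will be calculated on a per patient basis, averaged across the cohort". Each patient's own monthly rate therefore counts once, whatever the length of follow-up.

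The period is on-treatment. In section 9.1 patients "will be followed through the earliest of the following: health plan disenrollment, index therapy discontinuation, switch to another anticoagulant", or to study end. The same section sets the index date by the "first apixaban or LMWH prescription on or within the 30 days following a VTE diagnosis will be termed as the index date", so the clock starts 0 to 30 days after the VTE. Section 9.1.1 starts it one day later: "Patients will be followed from the day after the index date through the earliest of the following". The one-month minimum is a minimum of enrollment, not of time on drug. Section 9.2 asks for at least 14 days of LMWH use and states no minimum for apixaban.

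Section 9.3.1 tabulates "Follow up duration in months (mean, SD, median, IQR" and the numbers censored for switching and for discontinuation. In section 9.7 the weights model the probability of treatment received. The gamma GLM for all-cause cost is given as an example, with up to four models still to be agreed. No fixed window, cost by interval since index, or adjustment for censoring is planned, and section 9.9 does not list the issue as a limitation.

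**The concern.** Dividing by days and multiplying by 30 gives both cohorts the same unit of time. It does not give them the same part of the disease course. A patient followed for two months contributes the average of months 1 and 2; a patient followed for a year contributes the average of months 1 to 12. If cost per day is not constant over that course, these averages differ for a reason unrelated to the drug's effect on cost.

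Time on drug can differ between an oral and an injected anticoagulant, and it is known only after treatment starts. Weighting on baseline characteristics balances who starts each drug, not how long they stay on it. At stake is whether a difference in mean PPPM, or a cost ratio modelled on PPPM, can be read as a difference in cost between the drugs. The planned tables would show a difference in follow-up duration but not how much of the PPPM difference it explains.

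**Working it through.** **The plan's own figure.** Section 9.3.2 works an example "with 60 days of follow-up, the PPPM will be calculated as" 10,000/60 × 30 = 5,000 USD. This reproduces exactly.

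**Mechanism with fixed durations.** Assume one cost curve for every patient: 15,000 USD in the first 30 days and 7,500 USD per 30 days after that. For D ≥ 30 days, PPPM = [15,000 + 7,500 × (D − 30)/30] / D × 30.

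- D = 30: 15,000
- D = 60: 22,500/60 × 30 = 11,250
- D = 90: 30,000/90 × 30 = 10,000
- D = 180: 52,500/180 × 30 = 8,750

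The ratio of 90 to 180 days is 10,000/8,750 = 1.14, although both patients follow the same curve.

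**Cohort means with the planned estimator.** Assumptions, none of them from the documents: follow-up T = 1 + an exponential with mean m − 1 months (minimum one month, mean m); month 1 since index costs k times a later month; later months cost 1 unit; the curve is the same in both cohorts.

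- One patient's PPPM is (k + T − 1)/T = 1 + (k − 1)/T.
- The cohort mean is 1 + (k − 1) × E[1/T].
- E[1/T] is 0.461 for m = 3, 0.386 for m = 4, 0.335 for m = 5 and 0.299 for m = 6.
- For k = 2 and 3 versus 6 months: 1.461/1.299 = 1.13.

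Ratio of mean PPPM, shorter over longer cohort, true ratio 1.00:

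| Mean follow-up (months) | k = 0.5 | k = 1 | k = 1.25 | k = 1.5 | k = 2 | k = 3 |
|---|---|---|---|---|---|---|
| 3 vs 6 | 0.90 | 1.00 | 1.04 | 1.07 | 1.13 | 1.20 |
| 4 vs 6 | 0.95 | 1.00 | 1.02 | 1.04 | 1.07 | 1.11 |
| 5 vs 6 | 0.98 | 1.00 | 1.01 | 1.02 | 1.03 | 1.05 |

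Pooling total cost over total time does not remove the effect: for 3 versus 6 months and k = 2 it gives (1 + 1/3)/(1 + 1/6) = 1.14.

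**Sensitivity to the start of the clock.** A separate simulation used the 15,000/7,500 curve, a 14-day minimum and mean durations of 90 versus 180 days. It gave 11,459 versus 10,115 USD, ratio 1.13. Starting the clock 15 days into the curve gave 9,794 versus 8,956 USD, ratio 1.09. The effect shrinks but remains.

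**Aligned periods.** In the 1.13 example, mean cost per 30-day interval among patients still observed was 15,000 and then 7,500 USD in each of months 2 to 6, in both cohorts. The six-month totals were 52,500 and 52,500 USD, ratio 1.00.

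**Could it reach significance?** At the 1,867 per cohort of section 9.5, a spurious 10% difference has z = 0.10/(CV × √(2/1,867)). For an assumed coefficient of variation of 1.0, 1.5 or 2.0, it reaches two-sided p < 0.05 in 86%, 53% or 33% of studies (weighting ignored).

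**The case against.** - **Both conditions lie outside the documents.** They give no cost-by-time profile and no persistence by cohort. This stands. A reader might infer that a difference in persistence is enough by itself to create a cost difference, or that the plan favours a particular drug. The documents support neither: flat costs give a ratio of 1.00, and the direction depends both on which cohort stays on drug longer and on whether costs fall or rise.
- **Early costs are partly outside the window.** A reader might take follow-up to start at the VTE itself and so to include the costliest days. It starts at the first fill or the day after, and section 9.3.1 lists the cost of an index VTE hospitalization as a baseline item. This weakens the case for strong front-loading but does not make cost constant.
- **The GLM is not fixed.** A reader might conclude that the modelled cost ratio is certain to be biased. Section 9.7 only says such a model may be used. Follow-up duration is also listed among the demographic characteristics, which are candidate covariates. However, the plan does not commit to including it, and adjusting for a post-index variable would not be a clean repair.
- **This is a choice of estimand.** Mean monthly cost while on treatment is a definable quantity, and the plan is open that follow-up varies. A fixed-horizon total with censoring weights answers another question: cost had patients stayed on drug. This argues for keeping PPPM. It does not make PPPM a like-for-like comparison when periods differ.

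**Conclusion.** The point holds as a conditional one. Whole-period PPPM is not a clean comparison of drug cost unless cost per day is constant after index or time on drug is the same in both cohorts. The plan assumes neither explicitly and has no analysis that would show a failure of either. Baseline weighting does not address it.

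Under the assumptions in the table, the spurious ratio runs from 0.90 to 1.20 for mean follow-up of 3 versus 6 months, and from 0.98 to 1.05 for 5 versus 6 months. These figures show what is possible; they do not predict this study's result. The change is worth making because it is inexpensive and bears on how a primary result may be read. It does not show that the planned measure is invalid or must be replaced.

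**What to change.** In sections 9.3.2 and 9.7:

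1. Keep whole-period PPPM as planned.
2. Pre-specify an IPTW-weighted comparison of all-cause cost by interval since index (month 1, months 2–3, months 4–6) among patients still under follow-up.
3. Pre-specify cumulative cost over a common fixed window, for example 3 and 6 months, by summing the interval means, with a supporting version that uses inverse-probability-of-censoring weights.
4. State that a PPPM difference will be read as a cost difference between drugs only if the common-window comparison agrees.

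The cost is added text and moderate programming on data already extracted. Later intervals hold fewer patients, so longer windows are less precise. Patients still under follow-up may be a selected group, and the censoring weights rely on measured covariates explaining discontinuation and switching. Adding these as supporting analyses leaves the primary endpoint unchanged. Making the fixed-window result primary would be a major change to the primary analysis, which section 9.7 says belongs in a protocol amendment.

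### An outpatient visit coded for a bleed shortly before admission for that bleed is scored as a separate CRNM event, so one bleed enters both bleeding endpoints

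*Combined protocol and SAP*

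**What the plan says.** All the outcome rules are in protocol section 9.3.3.

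- Major bleeding is identified from inpatient stays: "Major bleeding will be defined by primary discharge diagnosis in the inpatient setting, including GI bleeding, intracranial hemorrhage (ICH), and other major bleeding".
- CRNM bleeding has two limbs. The inpatient limb takes secondary-position codes and carries an exclusion ("excluded if major bleeding occurred during the same hospitalization"). The outpatient limb reads "An outpatient encounter with a diagnosis code for GI bleeding and other selected noncritical types/sites of bleeding" and carries no exclusion and no time window.
- One rule for the CRNM analysis works across encounters: "Any CRNM bleeding events (as described above) that follow a major bleeding event (described above) will not be included".
- The event count takes in both settings: "Number of CRNM bleeding events (denoted by inpatient or outpatient events that meet the definition above".
- CRNM cost starts at the first CRNM event: "CRNM bleeding-related medical costs will be defined as hospitalization costs or outpatient costs associated with the first CRNM bleeding as defined above". It then adds later CRNM costs, including inpatient stays with the code in primary or secondary position. Major-bleeding cost starts at the first major-bleeding hospitalization and adds later bleeding costs.

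For the index VTE, section 9.1.1 does link a visit to the admission that follows it: "Qualifying outpatient encounters followed by qualifying inpatient encounters within 7 days will be considered an inpatient VTE event", with an exception if study treatment began between the two encounters. Section 9.3.3 has no such link for bleeding.

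**The concern.** GI bleeding qualifies under both endpoints, separated only by care setting and code position. A patient may be seen in the office with a GI bleed and admitted for it a day later. That is one bleed, and it proved to be major. The priority rule looks only forward from the major bleed, so the presenting visit remains as a CRNM event.

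The CRNM endpoint would then contain some bleeds that are not non-major. The outcomes affected are the proportion with CRNM bleeding, the number of events, time to first event (which becomes time to the presenting visit), and CRNM-related HCRU and cost. Event-related cost is the second primary objective in section 8, and event-related HCRU is a secondary objective. Because the added CRNM events scale with major bleeding, a cohort difference in major bleeding can pass into the CRNM comparison.

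**Working it through.** **Reading the rules against cases**

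1. Office visit on 1 June coded GI bleed; admission on 2 June with GI bleed as primary diagnosis. The visit meets the outpatient limb. It is not in the same hospitalization and does not follow the major bleed. Result: one CRNM event and one major bleed.
2. Admission on 2 June, clinic visit coded GI bleed on 9 June. The visit follows the major bleed and is dropped. Result: major bleed only, as intended.
3. Admission with a bleed as primary diagnosis and a noncritical-site code in secondary position. The same-hospitalization exclusion applies. Result: major bleed only, as intended.
4. Outpatient encounter on the day of admission. The text does not say whether this follows the major bleed.

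In case 1 the cost of the visit goes to CRNM and is absent from major-bleeding cost, which begins with the hospitalization. Whether the admission is also costed as CRNM is unclear. The cost rule for later CRNM events admits primary-position inpatient codes, which are the marker of a major bleed.

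**Illustration of the effect on the cohort comparison**

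The plan states no bleeding rates, so there is no figure of its own to reproduce. The following inputs are assumed:

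- true CRNM proportion c = 10% in both cohorts;
- major bleeding m = 3% with apixaban and 5% with LMWH (the direction follows the rationale in section 7; the values are not from the documents);
- share f of major bleeds with a bleed-coded outpatient visit beforehand: 10%, 30% or 50%, equal in both cohorts;
- CRNM and major bleeding independent.

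Observed CRNM proportion = c + f × m × (1 − c).

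| f | Apixaban | LMWH | Risk ratio |
|---|---|---|---|
| 0% | 0.1000 | 0.1000 | 1.00 |
| 10% | 0.10 + 0.1 × 0.03 × 0.9 = 0.1027 | 0.10 + 0.1 × 0.05 × 0.9 = 0.1045 | 0.98 |
| 30% | 0.10 + 0.3 × 0.03 × 0.9 = 0.1081 | 0.10 + 0.3 × 0.05 × 0.9 = 0.1135 | 0.95 |
| 50% | 0.10 + 0.5 × 0.03 × 0.9 = 0.1135 | 0.10 + 0.5 × 0.05 × 0.9 = 0.1225 | 0.93 |

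If m and f are equal in the two cohorts, the same quantity is added to both and a true ratio of 1.00 stays at 1.00.

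**The case against.** The strongest reply is that the gap is narrow and its size unknown. Most of that stands.

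- A reader might infer that the hierarchy acts only on CRNM events after a major bleed. It does not: the same-hospitalization exclusion also operates. That exclusion belongs to the inpatient limb, however, and does not reach an earlier outpatient visit.
- A reader might extend the point to every ER presentation. Section 9.3.2 defines its ER category as visits without hospital admission, so an ER visit that ends in admission is probably part of the stay. The clear cases are office, clinic and ER-only visits.
- The outpatient limb covers GI and selected noncritical sites, so an outpatient intracranial hemorrhage code should not count as CRNM. The code lists are in a separate file, and the exact overlap cannot be checked.
- A reader might infer a large, established inflation of CRNM rates. Every input to such a figure is assumed. Independence is assumed too: if patients with a major bleed more often have other CRNM events, fewer patients are added. Inflation of the level is also not the same as bias between cohorts.
- No composite of the two bleeding endpoints is planned, so no bleeding total is double counted. Total all-cause cost, the first primary objective, does not depend on how a bleed is labelled.
- The 7-day rule in section 9.1.1 classifies the setting of a qualifying event, not an outcome. It is an analogy and does not establish 7 days as the right window for bleeding.

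None of this supplies a rule for the visit before the admission, and the text contains none.

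**Conclusion.** The point holds as a defect in a stated classification rule. Followed literally, section 9.3.3 books one bleed under two endpoints when a bleed-coded outpatient visit shortly precedes the major-bleeding admission, and it leaves that visit out of major-bleeding cost. The affected outcomes are confined to CRNM patients, counts, time to first event, HCRU and cost, and to major-bleeding-related cost and HCRU.

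The frequency cannot be determined from the documents. The movement of the CRNM risk ratio to between 0.98 and 0.93 rests wholly on the assumed rates above and needs a cohort difference in major bleeding (or in the share of presenting visits). It would also be tempting to conclude that the admission is certainly costed twice. The documents do not settle this: the cost rule could be read to allow it, while the exclusion of primary-position major bleeds from CRNM could be read to prevent it. The change is worth making because it is cheap and concerns part of a primary objective.

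**What to change.** Add to section 9.3.3: post-index outpatient encounters with a bleeding code on the day of a major-bleeding admission, or within a prespecified window before it (for example 7 days, by analogy with section 9.1.1), and not before the index date, are part of that major bleeding event and are not CRNM events.

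Amend the cost paragraph of the same section so that:

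- these visits count in major-bleeding-related cost and HCRU, which now begin with the hospitalization;
- a major-bleeding admission is not also costed as CRNM.

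Add a sensitivity analysis with a shorter and a longer window. Before any cohort comparison, count the visit-and-admission pairs in the pooled data, so that the size of the problem is known.

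The cost is a few sentences, a small programming step and, if the sponsor regards this as a major change to a primary endpoint definition, the protocol amendment that section 9.7 calls for. The downside is that a truly separate minor bleed inside the window is absorbed into the major event; the sensitivity analysis shows how much depends on that choice.
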